### 1.3.4 Rationale for osimertinib neoadjuvant clinical trial

Access to patient tissue during the initial acute period of EGFR TKI treatment will be critical to defining the molecular and cellular mechanisms that underlie incomplete responses to EGFR TKI therapy. The availability of such tissue is incredibly limited, as EGFR TKI treatment is not standardly given prior to surgical resection of early stage NSCLCs.

Induction therapy with platinum-based chemotherapy given prior to surgical resection for patients with resectable lymph node-positive NSCLC is a safe and acceptable practice [29]. The role of EGFR TKI therapy as induction therapy for patients with EGFR-mutant NSCLC remains incompletely explored. In an unselected study of 50 patients with stage I or II NSCLC treated with gefitinib, 17 of 21 patients found to have activating EGFR mutations in their resected tumor specimens had a radiographic response to treatment [30]. In a separate study of an enriched

population of 60 non-squamous patients with early stage lung cancer treated with erlotinib for 21 days prior to surgery, patients with EGFR-activating mutations (n=7), 40% (3 of 7) had a pathological response with >50% tumor necrosis at the time of resection. In contrast, only 23% (8 of 35 patients) with WT EGFR exhibited >50% necrosis in their tumors at the time of resection [25]. While these results suggest that neoadjuvant therapy may be beneficial to patients with EGFR-activating mutations prior to surgery, a prospective trial in pre-selected EGFR-mutant lung cancer patients has not been performed.

We hypothesize that neoadjuvant treatment with osimertinib, an EGFR TKI that targets T790M in addition to common activating mutations in EGFR, will improve patient responses to induction therapy. Furthermore, the neoadjuvant design of this trial will allow us to perform comprehensive molecular analyses on tumor specimens pre-treatment and after initial response to osimertinib. We anticipate that this information will allow us to define mechanisms of incomplete initial response to osimertinib and facilitate development of rational companion therapies that when combined with osimertinib in the first line setting could result in more complete and durable responses for patients.

#### 1.4 Correlative Studies

[figure not shown]
Biopsies for tissue sampling will be obtained as described in detail in study procedures and as summarized here. A fresh tissue biopsy will be required prior to enrollment, permitting a baseline analysis.

Peripheral blood samples will be drawn for correlative studies at enrollment, serially during therapy, and following surgical resection. This tissue and blood collection will allow for serial assessment of correlative studies, in order to better understand mechanisms of disease persistence and resistance during treatment with EGFR TKI therapy.

Tissue and peripheral blood sample analysis will be carried out in collaboration with the [name] Lab (UCSF) and the Chan Zuckerberg Biohub. Organoid generation will be carried out through collaboration with the [name] Lab (Stanford University). Patient-derived xenografts (PDXs) generation will be carried out at the UCSF Tissue Core. Circulating tumor DNA (ctDNA) analysis will be performed in collaboration with Guardant Health or the Chan Zuckerberg Biohub.

##### 1.4.1 Exome and transcriptome sequencing

We will perform RNA sequencing and whole exome sequencing analysis on isolated cancer cell populations (Fig. 5) from pre-treatment tumor biopsy specimens, as well as tumor tissue acquired at the time of surgical resection (post-osimertinib). Gene Set Enrichment Analysis will be performed to identify osimertinib-induced changes in common cancer related pathways, including: RAS-RAF- MAPK, PI3K-AKT, WNT-  $\beta$ -catenin, JAK-STAT, HGF-MET, and IGF-1R, as well as emerging pathways of resistance (i.e. NF- $\kappa$ B and Hippo- YAP) [1, 46, 47]. We will determine whether there is a statistically significant increase in oncogenic/survival pathway related gene expression signatures in the post-osimertinib compared to the pre-treatment sample using established methods [48]. We will compare MPR rates in tumors that exhibit

**Figure 5. Schema of tumor and immune cell isolation strategy.** Pre-treatment tumor biopsies and post-surgical specimens will undergo single-cell dissociation and FACS analysis to isolate tumor cells CK+CD45+CD31+, CD4+ and CD8+ T-cells, and Tumor Associated Macrophages (TAMs). Exome and RNA sequencing will be performed

specific oncogenic/survival pathway activation post-osimertinib treatment compared to tumors that do not. Immunohistochemistry (IHC) analysis will be performed on pre-treatment and post-surgical specimens to confirm pathway activation identified by transcriptional analysis (i.e. phosphorylated-ERK (indicative of MAPK signaling), phosphorylated-AKT (indicative of PI3K signaling) or nuclear NF- $\kappa$ B (RELA), or beta-catenin expression).

#### 1.4.2 Immune profiling

We will assess for shifts in the cellular make-up of the tumor microenvironment induced by osimertinib treatment by performing single cell dissociation and fluorescence associated cell sorting (FACS) on fresh pre-treatment tumor biopsies and post-osimertinib tumor resection specimens. Using FACS gating strategies established and validated by the [name] lab at UCSF [49], we will isolate CD45+ immune cells and determine how osimertinib treatment alters the proportions of cells that make up the lymphoid (CD4+ and CD8+ T cells, Tregs, NK cells, B cells) and myeloid (macrophages, neutrophils, mast cells, dendritic cells) compartments. We will then use RNA-Seq to assess the transcriptional profiles of populations of TAMs, CD4+ and CD8+ T Cells (Fig. 5). We hypothesize that osimertinib treatment will induce a pro-tumor immune microenvironment that allows for tumor cell persistence. Specifically, we will assess the polarization of TAMs by assessing the mRNA expression profiles of genes classically associated with TH1-skewed (i.e. TNF- $\alpha$ , IL-6, IL-12p40, and IL-1 $\beta$ , and Nos2) and TH2-skewed polarization (i.e. ARG1, TGFB, CD163, CD206), many of which are targets of NF- $\kappa$ B transcriptional activation[50]. We will also investigate whether osimertinib affects T-cell phenotypes. CD4+ T cells will be assessed for the expression of genes indicative of TREG, TH1, TH2, or TH17 activity (i.e. GATA3, T-bet, FOXP3, IFN $\gamma$ , IL-4, IL-13, IL-10, and IL-17a)[50], and CD8+ T cells will be assessed for expression of cytotoxic effector molecules (IFN $\gamma$ , GRZA, GRZB, and PRF1)[50]. Finally, tumor cells and infiltrating immune cells will be assessed for shifts in PD-1 and PD-L1 expression (by RNA-Seq and IHC), a phenomenon that has been linked to NF- $\kappa$ B activity[41], and which may indicate changes in anti-tumor immunity induced by osimertinib. When possible, we will perform single cell RNA-sequencing on tumor biopsy and resection specimens at the Chan Zuckerberg Biohub.

#### 1.4.3 Derivation of patient-derived xenografts and organoids

When adequate tissue is available, PDXs and organoids derived directly from patients' resected tumors will be generated, as previously described (23). PDX-bearing mice will be treated with osimertinib or osimertinib in combination with therapies (acquired through commercial vendors) that target the putative resistance mechanisms identified, including tumor cell intrinsic or extrinsic targets. PDXs that are generated will be shared with AstraZeneca.

#### 1.4.4 Peripheral Blood circulating tumor DNA Collection

Serial peripheral blood and plasma samples will be stored for ctDNA analysis, and changes in peripheral immune cells.

## 2 Objectives of the Study

### 2.1 Primary

- To evaluate the efficacy of osimertinib as neoadjuvant therapy in patients with surgically resectable EGFR-mutant NSCLC.

### 2.2 Secondary

- To evaluate the safety of osimertinib given as neoadjuvant therapy in early stage EGFR-mutant NSCLC patients.
- To evaluate whether neoadjuvant osimertinib treatment increases the frequency of

tumors that are unresectable due to AEs or PD.

- To evaluate secondary measures of clinical efficacy in early stage EGFR-mutant NSCLC patients treated with osimertinib induction therapy.

## 2.3 Exploratory

- To evaluate long-term measures of efficacy in patients treated with osimertinib neoadjuvant therapy.
- To explore tissue and cell-free biomarkers that may be predictive of response or primary resistance to osimertinib neoadjuvant therapy.

## 2.4 Endpoints

### 2.4.1 Primary Endpoint

- To determine the MPR rate, defined as  $\leq 10\%$  viable tumor present histologically in the resected tumor specimen as has been previously defined.

### 2.4.2 Secondary Endpoints

- Radiographic decrease in maximum tumor diameter
- DpR
- 5-year DFS
- 5-year OS
- Complete pCR
- Treatment-emergent AEs, laboratory abnormalities and ECG abnormalities as determined by National Cancer Institute Common Toxicity Criteria (NCI-CTC) version 4.03 by investigator
- Rate of conversion to inoperable status due to treatment-related toxicity or PD
- Rate of surgical complications occurring prior to the end of treatment visit

### 2.4.3 Exploratory Endpoints

- Evaluate for adverse pathologic outcomes including pathologic upstaging as compared to clinical staging by pre-operative scans, rate of LVI, and rate of positive margins on resection specimens.
- Evaluate genomic and transcriptional changes on baseline and resected tumor specimens.
- Evaluate changes in immune cell infiltration on baseline and resected tumor specimens.
- Serial peripheral blood collection for exploratory biomarker assessment
- Changes in ctDNA

[figure not shown]
## 3 Study Design

### 3.1 Characteristics

This is a Phase 2, single arm, open-label, multicenter study evaluating the safety and efficacy of osimertinib administered orally daily to patients with stage I-IIIa, EGFR-mutant NSCLC who are planning to undergo surgical resection of their cancer.

Patients will undergo a research biopsy for correlative studies during screening prior to starting osimertinib treatment. Treatment will consist of osimertinib 80 mg by mouth daily in 28 day cycles given as neoadjuvant therapy. Patients may receive a second cycle of osimertinib at investigator's discretion. Patients will undergo serial assessments for anti-tumor efficacy and drug safety. The last dose of study drug will occur 3-7 days prior to planned surgical resection, which will occur within 14 days of the patient's most recent disease assessment scan.

**Study Schema:**

**3.2 Number of Participants**

27 evaluable patients will be enrolled in the study.

**3.3 Eligibility Criteria**

Patients must have baseline evaluations performed prior to the first dose of study drug and must meet all inclusion and exclusion criteria. In addition, the patient must be thoroughly informed about all aspects of the study, including the study visit schedule and required evaluations and all regulatory requirements for informed consent. The written informed consent must be obtained from the patient prior to enrollment. The following criteria apply to all patients enrolled onto the study unless otherwise specified.

**3.3.1 Inclusion Criteria**

1. Males and females ≥18 years of age.
2. Histologically or cytologically confirmed NSCLC, performed on a biopsy that occurred within the last 90 days. This biopsy can be deferred if the procedure is deemed to represent an unacceptable safety risk to the patient by the Principal Investigator and as long as the patient has a prior biopsy showing non-small cell lung cancer.
3. Documented activating EGFR mutation (Exon 19 deletion, T790M, or L858R) on tumor samples by Clinical Laboratory Improvement Amendments (CLIA)-approved test.
4. Patients treated with osimertinib or another EGFR TKI (including erlotinib, afatinib, gefitinib, & rociletinib) are eligible if they received no more than 28 days of treatment, and if there is no evidence of grade 2 or greater treatment adverse events possibly related to treatment with the EGFR TKI.
5. PET-CT (computerized tomography) within the last 60 days showing radiographic stage I to IIIa lung cancer (mediastinal staging biopsy is allowed but not required).
6. Brain magnetic resonance imaging (MRI) (or CT if contraindication to MRI) within the last 60 days showing no evidence of metastatic disease.
7. Documentation that the patient is a candidate for surgical resection of their lung cancer by an American Board of Thoracic Surgery certified surgeon.

8. The patient must have a tumor size  $\geq 1$  cm in its longest diameter.
9. Eastern Cooperative Oncology Group (ECOG) performance status of 0-1.
10. Any unresolved toxicities from prior therapy greater than CTCAE grade 1 at the time of starting study treatment, with the exception of alopecia and grade 2 prior platinum-therapy-related neuropathy is allowed
11. Adequate organ function:
  - Hepatic Function:
    - Aspartate aminotransferase (AST) and alanine aminotransferase (ALT)  $\leq 2.5$   $\times$  upper limit of normal (ULN).
    - Bilirubin  $\leq 1.5 \times$  ULN, (Patients with documented Gilbert's syndrome and conjugated bilirubin within the normal range may be allowed into the study. In this event, it will be documented that the patient was eligible based on conjugated bilirubin levels).
  - Electrolytes: Potassium, magnesium, and calcium within normal range, patients may receive supplements to meet this requirement.
  - Hematologic Function:
    - Leukocytes  $> 3,000/\text{mCL}$
    - Hemoglobin (Hgb)  $\geq 9$  g/dL, with no blood transfusions in the 28 days prior to study entry
    - Absolute neutrophil count  $> 1,500/\text{mCL}$
    - Platelets  $> 100,000/\text{mCL}$
  - Renal Function: CrCl  $> 50$  mL/min for patients with SCr  $> 1.5 \times$  ULN.
12. Ability to swallow oral medications
13. Women of childbearing potential must have a negative serum pregnancy test within 3 days prior to the first dose of study treatment and agree to use highly effective contraception, during the study and for 90 days following the last dose of osimertinib
  - Women of Childbearing Potential (WoCBP): Women between menarche and menopause who have not been permanently or surgically sterilized and are capable of procreation.
  - Women NOT of Childbearing Potential: Women who are permanently or surgically sterilized or postmenopausal (definitions below):
    - Permanent sterilization includes hysterectomy and/or bilateral oophorectomy and/or bilateral salpingectomy but excludes bilateral tubal occlusion. Tubal occlusion is considered a highly effective method of birth control but does not absolutely exclude possibility of pregnancy. (The term occlusion refers to both occluding and ligating techniques that do not physically remove the oviducts).
      - Women who have undergone tubal occlusion should be managed on trials as if they are WoCBP (e.g. undergo pregnancy testing etc., as required by the study protocol)
      - Women will be considered postmenopausal if they are amenorrhoeic for 12 months without an alternative medical cause. The following age-specific requirements apply:
        - Women under 50 years old will be considered postmenopausal if they have been amenorrhoeic for 12 months or more following cessation of exogenous hormonal treatments and with luteinizing hormone and follicle-stimulating hormone levels in the postmenopausal range
        - Women over 50 years of age will be considered postmenopausal if they have been amenorrhoeic for 12 months or more following

cessation of all exogenous hormonal treatments

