Primary Objective	To evaluate the efficacy of osimertinib as neoadjuvant therapy in patients with surgically resectable EGFR-mutant NSCLC. The primary endpoint of the study will be MPR rate defined as $\leq 10\%$ viable tumor present histologically in the resected tumor specimen.

Secondary Objectives	
1. To evaluate the safety of osimertinib given as neoadjuvant therapy in early stage EGFR-mutant NSCLC patients
 
2. To evaluate whether neoadjuvant osimertinib treatment increases the frequency of tumors that are unresectable due to adverse events (AEs) or PD.
 
3. To evaluate secondary measures of clinical efficacy in early stage EGFR-mutant NSCLC patients treated with osimertinib induction therapy. Secondary endpoints of efficacy will include radiographic decrease in maximum tumor diameter, complete pathologic response rate, 5-year disease-free survival (DFS), and 5-year overall survival (OS).

Study Design	
This is a phase II multi-institution (UCSF and participating sites), single-arm, open-label clinical trial of neoadjuvant osimertinib in Stage I-IIIa EGFR-mutant lung cancer patients who are planning to undergo surgical resection of their lung cancer.
 
A total of 27 evaluable subjects will be enrolled in the study. This will provide 87% power to detect a MPR rate of 50% among patients receiving osimertinib induction therapy as compared to a null hypothesis response rate of 22%, which has been observed for neoadjuvant chemotherapy in unselected NSCLC populations [23, 24], at the 5% significance level.
 
Patients will receive the study drug for a minimum of 1 cycle prior to surgery (28 days). ORR will be determined by CT scan prior to surgery. Investigators will have the option to give a second cycle of study drug prior to surgery if clinically indicated.

Number of patients	27 patients will be enrolled.
Duration of Therapy	Patients may continue treatment for up to 70 days from the time of study entry.
Duration of Follow-up	Follow-up for individual participants will be up to 5 years.
Duration of study	The study will reach completion 48 months from the time the study opens to accrual.
Study Drugs	Osimertinib 80 mg per os (PO) daily

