    - Any factors that increase the risk of QTc prolongation or risk of arrhythmic events such as heart failure, electrolyte abnormalities (including: Serum/plasma potassium < LLN; Serum/plasma magnesium < LLN; Serum/plasma calcium < LLN), congenital long QT syndrome, family history of long QT syndrome or unexplained sudden death under 40 years of age in first degree relatives or any concomitant medication known to prolong the QT interval.
  8. Treatment with prohibited medications (concurrent anticancer therapy including chemotherapy, radiation, hormonal treatment [except corticosteroids and megestrol acetate], or immunotherapy) ≤ 14 days prior to treatment with osimertinib.
  9. Any evidence of severe or uncontrolled systemic diseases, including uncontrolled hypertension and active bleeding diatheses, which in the investigator's opinion makes it undesirable for the patient to participate in the trial or which would jeopardize compliance with the protocol, or known active infection including chronic active hepatitis B virus (HBV), hepatitis C virus, and HIV. Screening for chronic conditions is not required. Patients with chronic HBV with negative HBV viral load on appropriate antiviral therapy will be permitted, if able to continue appropriate antiviral therapy throughout treatment period.
  10. Active tuberculosis.
  11. Signs or symptoms of infection within 2 weeks prior to first day of study.
  12. Therapeutic oral or IV antibiotics within 2 weeks prior to first day of study treatment:
    - Patients receiving prophylactic antibiotics (e.g., to prevent a urinary tract infection or chronic obstructive pulmonary disease exacerbation) are eligible.
  13. Class II to IV heart failure as defined by the New York Heart Association functional classification system.
  14. Patients with known coronary artery disease, congestive heart failure not meeting the above criteria, or LVEF <50% must be on a stable medical regimen that is optimized in the opinion of the treating physician, in consultation with a cardiologist if appropriate, to be eligible.

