#### 6.1.1.2 Screening Assessments

The Screening procedures and assessments must be completed within 30 days prior to Day 1 Visit, except for, pregnancy testing, which must be completed within 3 days prior to Day 1.

- IR-guided core biopsy tumor specimen of a soft tissue lesion within 30 days prior to starting study drug for correlative studies. A repeat biopsy is permitted if quantity of tissue is insufficient. This biopsy can be deferred if the procedure is deemed to represent an unacceptable safety risk to the patient by the principal investigator.
- If there was not enough archival tissue for a pre-screening EGFR mutation testing, this research biopsy will be used to obtain tissue for EGFR mutation testing as well as the correlative studies. EGFR mutation tests will be done at a local laboratory (UCSF or laboratories affiliated with participating sites) or investigator's choice of CLIA-approved laboratory.
- If there is enough archival tissue left over, it will be sent to Guardant (Redwood City) for DNA analysis.
- A physical examination will be performed and include an assessment of the following: general appearance, skin, head and neck (including ears, eyes, nose and throat), respiratory, cardiovascular, abdomen, lymph nodes, thyroid, musculoskeletal (including spine and extremities) and neurological systems.
- Vital signs
- Complete medical history, including history of prior treatments and any residual toxicity relating to prior treatment.
- Baseline conditions assessment
- Performance status (ECOG)
- Baseline medications taken within 30 days of Day 1.
- Complete blood cell count (CBC) with differential and platelet count
- Blood chemistry assessment, including:
  - Alkaline phosphatase (ALP), AST/ALT, total bilirubin, calcium, phosphorus, blood urea nitrogen (BUN), creatinine, total protein, albumin, fasting or non-fasting glucose, potassium, magnesium, sodium, chloride, bicarbonate.
- Coagulation assessment, including prothrombin time, partial thromboplastin time, international normalized ratio (PT/PTT/INR)

- Urinalysis
- For female patients, serum or urine pregnancy test within 3 days prior to the start of study drug
- Contraceptive counseling
- Confirmation of no evidence of metastatic disease by PET-CT and brain imaging (MRI or CT) within 60 days of Day 1.
- Disease assessment by CT of the chest, abdomen, pelvis (MRI acceptable if contraindications to CT) within 30 days of Day 1.

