### 6.5 Prohibited Medications Other anticancer therapy

Systemic anticancer therapy (chemotherapy, targeted therapy, biologic therapy, or radiation therapy), other than the osimertinib treatment, must not be given to patients while they are enrolled in the treatment portion of the trial. If such agents are required then the patient must be permanently discontinued from the treatment portion of the study.

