### 8.3.3 Secondary Analysis (or Analysis of Secondary Endpoints)

**5-Year DFS:** DFS will be calculated as 1+ the number of days from date of surgical resection to documented radiographic relapse/progression or death due to any cause over a period of 60 months. The Kaplan-Meier analysis will be used to calculate the median DFS with 95% confidence interval. 5-year DFS rate will be calculated as the percentage of patients who are disease free at 5 years. This will be calculated using the Kaplan-Meier method.

Assuming alpha of 0.05 and a set sample size of 27, as well as a null hypothesis of 50% 5-year DFS [53], we will have a power of 80% to detect a 25% increase in 5-year DFS.

**Objective Response Rate:** The objective response rate is defined as the best overall response recorded from the start of the treatment until time of surgery. The frequency and percentages of patients with a best ORR of CR, PR, SD, or PD will be determined. The objective response rate will be reported with 95% confidence intervals.

**Pathologic Complete Response Rate (pCR):** The pCR is defined as absence of (0%) viable tumor present histologically in the resected tumor specimen. Scoring for pathologic response is described above.

**5-Year Overall survival (OS) rate:** 5-year OS rate will be calculated using the Kaplan-Meier method. OS will be defined as the 1+ the number of days from surgical resection to death due to any cause over a period of 60 months. The Kaplan-Meier analysis will be used to calculate the median OS with 95% confidence interval.

**Depth of Response (DpR):** DpR will be defined as the percentage change in tumor burden by RECIST criteria at best response versus baseline imaging. DpR will be summarized using descriptive statistics and correlated with patient outcomes using hazard ratios via the Cox proportional hazards model.

**Safety and Tolerability:** AE terms recorded on the CRFs will be mapped to preferred terms using the MedDRA. Seriousness, severity grade and relationship to study treatment will be assessed by the investigator. Severity grade will be defined by the NCI CTCAE v4.03. Listings of AEs will be provided. Rate of conversion from operable to non-operative will be recorded as rate of patients initially assessed as surgically resectable, who are subsequently unable to undergo surgical resection due to either treatment-related AEs or PD. Rate of surgical complications occurring prior to the end of treatment visit will be recorded.

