### 8.3.4 Other Analyses/Assessments

#### Exploratory Analysis:

- We will record rates of adverse pathologic features including rates of positive margins, LVI, and pathologic upstaging (e.g., by T or N status) as compared to clinical staging based on pre-operative scans, for comparison to historical controls.
- We will perform RNA sequencing and whole exome sequencing analysis on isolated cancer cell populations from pre-treatment tumor biopsy specimens, as well as tumor tissue acquired at the time of surgical resection (post-osimertinib). Gene Set Enrichment Analysis will be performed to identify osimertinib-induced changes in common cancer related pathways, including: RAS-RAF-MAPK, PI3K-AKT, WNT-  $\beta$  catenin, JAK-STAT, HGF-MET, and IGF-1R, as well as emerging pathways of resistance (i.e. NF- $\kappa$ B and Hippo-YAP) [1, 46, 47]. We will determine whether there is a statistically significant increase in oncogenic/survival pathway related gene expression signatures in the post-osimertinib compared to the pre-treatment sample using established methods [48]. We will compare MPR rates in tumors that exhibit specific oncogenic/survival pathway activation post-osimertinib treatment compared to tumors that do not. IHC analysis will be performed on pre-treatment and post-surgical specimens to confirm pathway activation identified by transcriptional analysis (i.e. phosphorylated-ERK (indicative of MAPK signaling), phosphorylated-AKT (indicative of PI3K signaling) or nuclear NF- $\kappa$ B (RELA), or -  $\beta$  -catenin expression). Samples will be scored in a continuous manner and difference among time points will be determined by a two-tailed T-test.

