 C1D28 visit only for patients not receiving second cycle of osimertinib

 Optional second cycle as per investigator discretion. Those receiving second cycle osimertinib do not attend the C1D28 visit

 Screening biopsy within 30 days prior to C1D1. Tissue from screening biopsy and surgical resection will be used for correlative studies (see Section 1.4). If there is not enough tissue for pre-screening EGFR mutation testing, tissue from this biopsy will also be collected for EGFR mutation testing. This biopsy can be deferred if the procedure is deemed to represent an unacceptable safety risk to the patient by the principal investigator.

 Including CBC with differential and platelet count

 Including ALP, ALT/AST total bilirubin, calcium, phosphorus, BUN, creatinine, total protein, albumin, fasting or non-fasting glucose, potassium, sodium, chloride, bicarbonate. Magnesium required at screening only.

 Including PT/PTT/INR

 In women of child-bearing potential. At screening to be done within 3 days of C1D1.

 Imaging within 28 days prior to C1D1. If CT contraindicated, MRI acceptable

 If not be receiving second cycle of osimertinib

 Including documentation of AEs leading to inability to proceed with surgical resection and of surgical complications

 Optional research biopsy for patients who will be unable to undergo surgical resection, within 30 days of C1D28 or C2D28

 Dispensing of up to 14 days' supply osimertinib for treatment until pre-surgical washout period if will be proceeding to resection after first cycle of osimertinib.

 TTE is only required if the patient is proceeding to surgical resection following first cycle of osimertinib therapy. For patients receiving the second of cycle of osimertinib, TTE is optional except for patients with pre-existing risk factors as clinically indicated. .

 PET-CT and brain MRI (standard of care procedures) must be done within 60 days of C1D1 as part of inclusion criteria (see Section 3.3.1)

 During the first year after the EOT visit, assessment of survival status and subsequent care for NSCLC will occur every 3 months. From the first year following EOT visit up to the 5 years post-surgery, assessment of survival status and subsequent therapies will occur every 6 months via telephone or routine clinic visits.

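### Patients may enter after up to 28 days of an EGFR TKI, but depth of response, response rate and the paired tissue analyses have no rule for a baseline scan or biopsy taken after that exposure

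*Combined protocol and SAP*

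**What the plan says.** **Eligibility.** Criterion 4 in section 3.3.1 states that patients previously given osimertinib or another EGFR TKI "are eligible if they received no more than 28 days of treatment", provided they had no grade 2 or higher event possibly related to it. The criterion sets no washout and no limit on how recent the course may be.

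**Baseline windows.** All of them run from the study's own first dose. Section 6.1.1.2 asks for an "IR-guided core biopsy tumor specimen of a soft tissue lesion within 30 days prior to starting study drug for correlative studies" and for a CT within 30 days of Day 1. Appendix 1, footnote 10, gives "Imaging within 28 days prior to C1D1". Section 7.2.3 also sets a 28-day limit for baseline evaluations.

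**Analyses that use the baseline.** Section 8.3.3 defines DpR as the "percentage change in tumor burden by RECIST criteria at best response versus baseline imaging", and DpR then enters a Cox model. Objective response uses the baseline sum of diameters (section 7.2.2). In section 8.3.4, gene set enrichment analysis is meant to "identify osimertinib-induced changes in common cancer related pathways" by comparing the biopsy, labelled pre-treatment, with the resected tissue, labelled post-osimertinib. The IHC and FACS comparisons have the same form.

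**Primary endpoint.** Section 8.3.2 determines MPR in everyone given at least one dose, with no split by prior TKI.

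**Treatment length.** The Abstract says: "Patients may continue treatment for up to 70 days from the time of study entry". Section 3.4 allows up to two 28-day cycles plus up to two weeks awaiting surgery, with drug stopped 3 to 7 days beforehand.

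**The concern.** A patient who goes straight from 28 days of osimertinib into screening could have both the baseline CT and the research biopsy taken on drug. Section 4.1.1 puts steady state at about 15 days, so this exposure is not negligible. The plan would still treat the scan as the zero point for tumor change and the biopsy as untreated tissue.

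Two things are at stake. DpR and response rate would omit whatever shrinkage came before the baseline scan, and the mismeasured DpR would carry into the Cox model. The paired tissue comparison, which sections 1.3.4 and 1.4 give as a main reason for the neoadjuvant design, would compare treated tissue with treated tissue. Section 1.3.1 reports that NF-κB signaling is engaged rapidly once an EGFR inhibitor is started, so a biopsy after some weeks of TKI may already carry the change being sought.

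**Working it through.** **1. The plan's own figure.** Section 8.1.1 gives 87% power for N = 27, MPR 50% against 22%, at the 5% level. With an exact binomial rule, the smallest count with tail probability at or below 0.05 under 22% is 11: P(X ≥ 11 | 27, 0.22) = 0.0221 and P(X ≥ 11 | 27, 0.50) = 0.8761. (A cut-off of 10 gives 0.0549 under the null.) The 87% reproduces, so the sample size statement is not in question.

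**2. Effect on DpR for one patient.** Let d be the true change from before any TKI to surgery, and s the fraction of shrinkage already present at the baseline scan. The plan's DpR is (1 + d)/(1 - s) - 1. Sizes are assumed: 40 mm before any TKI and 26 mm before surgery, so d = 26/40 - 1 = -35.0%, a partial response under section 7.2.4.

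| Shrinkage before baseline scan | Baseline read | DpR under the plan | Category |
|---|---|---|---|
| 0% | 40 mm | 26/40 - 1 = -35.0% | PR |
| 10% | 36 mm | 26/36 - 1 = -27.8% | SD |
| 20% | 32 mm | 26/32 - 1 = -18.8% | SD |
| 30% | 28 mm | 26/28 - 1 = -7.1% | SD |

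In this example the category changes once s exceeds 1 - 0.65/0.70 = 7.1%.

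**3. Effect on the summaries.** Suppose k of 27 patients are affected as above; k is an assumption. Mean DpR moves by (k/27) times the individual error. At the small end (k = 3, s = 10%) this is 3/27 × 7.2 = 0.8 percentage points. At the large end (k = 8, s = 30%) it is 8/27 × 27.9 = 8.3 points. Each patient moved from PR to SD lowers the response rate by 1/27 = 3.7 points.

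**4. Exposure.** TKI-naive patients: from about 28 days (one cycle) to 56 + 14 - 3 = 67 days on drug. Prior-TKI patients: up to 28 + 67 = 95 days. At the low end, one prior day plus one cycle is 1 + 28 = 29 days.

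**5. Sensitivity of MPR.** Take k prior-TKI patients with MPR rate q and 27 - k others with rate p, and convolve the two binomials. The documents give neither k nor q, nor an explicit success rule; 11 or more of 27 is the cut-off from step 1. Without prior-TKI patients the chances are 0.022 (p = 22%) and 0.876 (p = 50%).

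| Chance of ≥ 11 of 27 | k = 3 | k = 5 | k = 8 |
|---|---|---|---|
| p = 22%, q = 35% | 0.034 | 0.044 | 0.064 |
| p = 22%, q = 50% | 0.051 | 0.083 | 0.155 |
| p = 50%, q = 35% | 0.838 | 0.808 | 0.758 |
| p = 50%, q = 65% | 0.909 | 0.927 | 0.949 |

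The result moves either way with q, and nothing in the documents fixes q.

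**The case against.** **The case for leaving the plan alone.** The affected group may be empty. Exclusion 8 (section 3.3.2) bars prohibited anticancer therapy "≤ 14 days prior to treatment with osimertinib", and section 6.5 lists as prohibited "Systemic anticancer therapy (chemotherapy, targeted therapy, biologic therapy, or radiation therapy), other than the osimertinib treatment". Read together, these could require 14 days off another TKI. A prior course could also be remote, since criterion 4 has no recency limit. The outcomes affected are secondary or exploratory, and too small a DpR understates the drug's effect. Treatment history is collected at screening, so these patients can be identified later.

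**What stands of it.** An on-drug baseline is permitted, not certain. But exclusion 8 does not name EGFR TKIs, and section 6.5 exempts osimertinib, so no washout is stated for the prior drug that matters most. Even with 14 days off, the baseline is not TKI-naive. Understating the effect may be called conservative for DpR and response rate. It is not so for the correlative work, whose purpose is to detect change, nor for a mismeasured covariate in a Cox model. Collecting the history does not help unless an analysis uses it.

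**Stronger readings that the documents do not support.**
- A reader might infer that the primary MPR result is biased upward. MPR is read on the resected specimen, and the pre-treatment biopsy is only an optional aid to the pathologist. Exposure already varies from about 28 to 67 days by design. Longer exposure could raise MPR; early resistance or a treatment gap could lower it.
- A reader might infer total exposure of 56 to 98 days for all such patients. That assumes exactly 28 prior days, where the text sets a maximum, and 98 = 28 + 70 counts the days off drug before surgery.
- A reader might infer that safety rates are biased low, because these patients enter only after tolerating a TKI. The selection is real, but the documents give nothing from which to size it.

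**Conclusion.** The point holds for DpR, objective response and the paired pre/post tissue analyses. Followed as written, the plan can use a scan or biopsy taken during or after TKI exposure as the untreated reference, with no rule to prevent it or account for it. For one affected patient, a true -35% can read as anything from -28% to -7%. Across the trial, the assumed cases shift mean DpR by 0.8 to 8.3 percentage points. These sizes rest on assumed tumor measurements, assumed earlier shrinkage and an assumed 3 to 8 affected patients. If no such patient enrolls, the effect is nil.

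The attenuation of the molecular and immune comparisons follows if the changes begin before the biopsy, as section 1.3.1 suggests for NF-κB; it cannot be quantified from the documents.

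For MPR the conclusion is limited: agents and exposure are mixed somewhat more than the design already mixes them, in an unknown direction. That justifies a sensitivity analysis, not a change to the primary analysis or the sample size.

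**What to change.** Leave criterion 4 as it is and change sections 8.3.2 to 8.3.4:

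1. Base the DpR and response-rate summaries, including the DpR Cox model, on TKI-naive patients. List prior-TKI patients separately, with agent, dates and cumulative exposure.
2. Base the paired pre/post sequencing, IHC and FACS analyses on TKI-naive patients. Include a prior-TKI patient only where a pre-TKI sample suitable for that assay exists.
3. Use a pre-TKI scan as the DpR or response baseline only in a labelled supplementary analysis of total TKI effect. As a main baseline it would credit osimertinib with shrinkage caused by a different TKI. It may also fall outside the 28-day limit in section 7.2.3, which must be reconciled with such an analysis and with the 30-day CT window in section 6.1.1.2.
4. Keep MPR in all dosed patients as the primary analysis, and prespecify MPR in TKI-naive patients as a sensitivity analysis.
5. The sponsor should reconcile criterion 4 with exclusion 8 and section 6.5, so that it is clear whether and how these apply to prior EGFR TKIs, osimertinib included.

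**Cost.** Plan wording, one extra table, and the agent and dates of prior TKI drawn from the treatment history already collected. The DpR, response-rate and paired analyses lose the prior-TKI patients: 3 to 8 of 27 (11% to 30%) in the cases assumed above, none if no such patient enrolls.
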